 in the study but after non-compliance and at least 3 documented, attempted contacts
 appropriately spaced 1-5 days apart, the family member will be considered LTF. Patients and
 family members who reach this status have no additional follow-ups or study requirements.
 Patients and family members who are assigned this status must be maintained on the
 enrollment log.
 - A family member who returns the study team's contacts within 1 week of last attempted contact may resume study participation.
 - A family member who has completed at least T1, T2, and T3 will be included in the overall target enrollment, even if deemed LTF for T4.
- Completed: defined as any family member who both consented and randomized to the study and completed T1-T4 (or at least 75% of the surveys). Family members and patients who reach this status have no additional follow-up or study requirements. Family members and patients who are assigned this status must be maintained on the enrollment log.

Protocol Version: 5.1 Dated: 13 June 2022 Page 13 of 42

Study data collection

Each consented family member will be asked to complete four surveys, as well as up to two meetings (for intervention group participants). Appendix 4 shows the timeline and acceptable time frames within which survey responses are allowed. Note that some latitude is provided given the possibility for weekends, etc.

- Baseline, Survey 1 (Day 1; up to 3 days allowed post-consent): this will occur generally on the day of consent. At this time, the following will occur:
 - App Registration
 - Survey 1 (T1) Completion
 - Randomization (if eligible)
- ICU Family Meeting for intervention group: The ICU attending will initiate a one-on-one family meeting to discuss the reported family needs. This is to occur prior to the completion of Survey 2 (T2).
- Survey 2: (Day 4; up to 4 days allowed post-randomization)
- Need-focused Palliative Care Family Meeting for intervention group: As noted above, this meeting will be triggered by a family member's T2 NEST score that is either ≥25 or higher than their T1 NEST score. The ICU attending and the Palliative Care team will meet with the family member together if at all possible to discuss the reported family needs. This meeting is to occur prior to the completion of Survey 3 (T3).
- Survey 3: (Day 8 up to 4 days allowed)
- Survey 4: (Day 90; up to 28 days allowed)

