Adverse events (AEs) generally would include extremely high distress levels (PHQ-9 score >25, GAD-7 score >20, PTSS score >34) or active suicidal ideation (i.e., endorsement of PHQ-9 suicidal ideation item plus a positive response to a branching logic item signifying active planning that would follow inquiring about a plan). A serious adverse event (SAE) would be a suicide attempt, a hospitalization, or death.

It is anticipated, in this study, for AEs to be extremely uncommon as it is a behavioral study. However, it is possible that participants could exhibit signs of and/or experience suicidal ideations with intent or thoughts of intent to act on such ideations. No other event, outside of suicidal ideation with intent or thoughts of intent to act on ideations will be considered an AE for this trial.

Like, AEs, it is not anticipated that SAEs will occur. However, for this study, an SAE would include a suicide attempt, a hospitalization (of family member), or death (of family member). All serious adverse events will be reported within the standard timelines required to the IRB, study sponsor, and/or DSMB, as appropriate and when applicable.

Protocol Deviations (PDs) and Unanticipated Problems (UPs)

Protocol deviations are errors made by study staff or deviations from plan made by study clinicians such as failure to conduct a family meeting. Unanticipated problems could consist of issues such as failure of the study staff to respond in a timely manner to suicidal ideation reported by a participant.

Given the nature of this study, it is anticipated that most enrolled family members will not complete their study surveys within the assigned protocol window. Additionally, it is expected that surveys may be missed as these are self-reported outcomes. As such, these will not be considered protocol deviations. Should other protocol deviations or unanticipated problems occur, they will be discussed with the PI, documented, and reported to the IRB, study sponsor, and/or DSMB, as appropriate and when applicable.

Period and Frequency for Event Assessment and Follow-Up

Protocol deviations and other unanticipated problems, as well as AEs and SAEs, will be recorded in the data collection system throughout the study.

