Appendix 3: Schedule of Events

	Day 0 (In-Hospital, Baseline)	Family Meeting (Day 0, +3 days)	Day 4 (+4 days)	Family Meeting (Day 4, +3 days)	Day 8 (+4)	Day 90 (+28 days)
Screening	Х					
Consent (a)	Х					
App Registration	Х					
T1 Survey (b)	Х					
Randomization (c)	Х					
T2 Survey (d)			Х			
T3 Survey (d)					X	
T4 Survey (d)						Х
ICU Physician Family Meeting (e)		Х				
Palliative Care Family Meeting (f)				X		
Data Entry (g)	х		Х		Х	
AE/SAE assessment (h)	х		X		Х	Х
Survival Status (i)		Х				Х
End of Study		Х				Х

- a) Study team is only able to approach family members (LARs) for consent once the ICU physician has marked the patient "approved" in the PCplanner web application (or if the ICU attending has opted out of approval for all patient/family dads).
- b) Survey 1, T1 is to be completed ideally on the day of consent, but within 72 hours.
- c) Family members are eligible for randomization to the study based on their NEST score at the completion of survey 1, T1 (> 10). Family members can be randomized to either the intervention or the control arm.
- d) The timing of completion of surveys T2, T3, and T4 are directly linked to the timing of completion of survey 1, T1. Family members will receive automated alerts notifying them of survey completion at each set time interval based on the completion of T1.
- e) The ICU Physician Family meeting occurs for any family member that is randomized to the intervention arm. The ICU physician in attendance will receive automated alerts notifying them of patient/family enrollment, the NEST score and associated results and daily reminders to complete the family meeting.
- f) Like the ICU Physician family meeting, the Palliative Care family meeting will occur for those individuals who are randomized to the intervention arm; however, only family members who receive a NEST score > 25 or > their T1 NEST score at the completion of T2 will illicit the Palliative Care family meeting. The ICU Physician is responsible for facilitating in the coordination of the Palliative Care family meeting.
- g) Data entry is to be completed within the study EDC, REDCap.
- h) AE/SAE assessment and survival status will be completed via EMR review and/or telephone interview.

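### Read literally, the lost-to-follow-up rule closes out a caregiver who is unreachable around T2 or T3 some 60 to 76 days before the day-90 survey opens

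*Combined protocol and SAP*

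**What the plan says.** The LTF status in section 5 (Study Procedures) applies to a caregiver who consented to take part "in the study but after non-compliance and at least 3 documented, attempted contacts" that are "appropriately spaced 1-5 days apart, the family member will be considered LTF". Non-compliance is not defined, and the rule is not tied to a particular survey. The consequence is that "family members who reach this status have no additional follow-ups or study requirements". The only way back is this: "A family member who returns the study team's contacts within 1 week of last attempted contact may resume study participation".

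Other passages bear on whether T4 survives an early LTF status:

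- The same LTF definition says that a caregiver with T1 to T3 done "will be included in the overall target enrollment, even if deemed LTF for T4". That uses the status for one survey only.
- The Completed status covers anyone who "completed T1-T4 (or at least 75% of the surveys"). Three of four surveys suffice, so T1, T2 and T4 without T3 would qualify.
- Appendix 3, note d: "The timing of completion of surveys T2, T3, and T4 are directly linked to the timing of completion of survey 1, T1". Alerts are automated on that basis.
- Appendix 4, by contrast, makes the T3 window depend on completion of T2.
- Section 8 (Aim 2) intends to interview caregivers at T4 whether or not the patient has survived. It treats loss to follow-up as a source of non-random missing data, and in a supplemental analysis it multiply imputes missing T4 data for caregivers of survivors.

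**The concern.** The 3-month PHQ-9, GAD-7 and PTSS are stated secondary outcomes, and T4 is their only long-term measurement. A caregiver may be silent in the first weeks because the patient is dying or because of distress, and may still be willing to answer at three months. The LTF rule runs on a clock of a few weeks that has no link to the T4 date, so a temporary silence can become a permanent loss.

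The missing values would be avoidable, because the study would have stopped asking. They could also be informative, because the reasons for early silence plausibly relate to the distress being measured. Only intervention caregivers have protocolized clinician meetings, so a difference between arms in who is lost is possible, though nothing in the documents shows it.

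**Working it through.** **1. The plan's own figures.** The documents give no time to LTF and no retention figure for T4. The nearest stated figure is the PHQ-9 calculation at day 8 (section 8: 2.33 units, SD 5.3, correlation 0.6, 80% power, 5% type I error, taken as two-sided).

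- SD of change = 5.3 × √(2 × (1 − 0.6)) = 4.74.
- n per arm = 2 × (1.960 + 0.842)² × 4.74² / 2.33² = 65, or 130 in total. This reproduces the plan.
- Dropout: 130 / 0.90 = 144.4, rounded up to 145. The planned 150 tolerates a loss of 1 − 130/150 = 13.3%.

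All of this concerns day 8, not T4.

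**2. When the rule closes a caregiver.** Let *s* be the day after which contacts begin and *g* the gap between contacts (1 to 5 days). Assume exactly three contacts, the first on day *s* + 1 (assumption). Then:

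- LTF day = *s* + 1 + 2*g*
- re-entry closes = LTF day + 7
- gap to T4 = 90 − closing day

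The text does not say whether contacts start after the due day or after the window closes, so both are shown. T2 is due on day 4 (window to day 8), T3 on day 8 (window to day 12), and T4 opens on day 90.

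| Contacts begin after | LTF day, g = 1 / 5 | Re-entry closes, g = 1 / 5 | Days before T4, g = 1 / 5 |
|---|---|---|---|
| T2 due day (4) | 7 / 15 | 14 / 22 | 76 / 68 |
| T2 window end (8) | 11 / 19 | 18 / 26 | 72 / 64 |
| T3 due day (8) | 11 / 19 | 18 / 26 | 72 / 64 |
| T3 window end (12) | 15 / 23 | 22 / 30 | 68 / 60 |

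Closure falls on day 14 to 30, which is 60 to 76 days before T4. The start assumption matters little:

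- First contact on the T2 due day itself: 4 + 2 + 7 = day 13, a gap of 77 days.
- First contact five days after the T3 window, at five-day spacing: 12 + 5 + 10 + 7 = day 34, a gap of 56 days.
- The rule says at least three contacts. Each further contact at five-day spacing adds 5 days.

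**3. What is left for the analysis.** Appendix 5 collects the three distress scales at T1, T3 and T4 only. A caregiver closed out after missing T3, or after missing T2 and so not reaching T3, has only baseline distress scores. Imputation or a mixed model then has little to work with.

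**4. Precision at T4.** T4 loss is an assumed range here. The day-8 PHQ-9 inputs are carried over to T4 (also an assumption), with 75 per arm randomized. The detectable difference is 4.74 × √(2/n) × (1.960 + 0.842).

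| T4 loss | n per arm | Power for 2.33 units | Difference detectable at 80% power |
|---|---|---|---|
| 10% | 67.5 | 0.815 | 2.29 |
| 20% | 60 | 0.768 | 2.42 |
| 30% | 52.5 | 0.712 | 2.59 |
| 40% | 45 | 0.645 | 2.80 |
| 50% | 37.5 | 0.567 | 3.07 |

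Even at 50% loss the detectable difference stays below the 5.0-unit MCID that the protocol cites. Bias is therefore a larger worry than precision.

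**The case against.** **The protocol may already intend T4 to go out.** Alerts run from T1, nothing says that LTF status switches them off, the status is used for T4 alone in one sentence, and the Completed rule accepts a missing T3. The Appendix 1 workflow and most of Appendix 4 are figures not shown in the available text, and a T4 rule could stand there. This has weight: it cannot be stated as fact that T4 is never sent. But the status definition says the opposite of what these passages suggest, and staff could follow either.

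**The trigger is narrower than it may look.** A reader might infer that one missed survey is enough, or that most caregivers will be caught, because "it is anticipated that most enrolled family members will not complete their study surveys within the assigned protocol window". Neither is supported. The rule needs non-compliance and at least three contact attempts. The quoted sentence is about lateness; on missed surveys the protocol says only that they may occur. A late caregiver who responds to a contact can continue, and planned dropout by day 8 is 10%.

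**The early end of the timing is debatable.** LTF on day 7 would fall inside the T2 window. The text neither defines such a caregiver as non-compliant nor rules it out. If contacts start only after a window closes, closure is on day 18 to 30, or 60 to 72 days before T4. The conclusion does not change.

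**Missing data are already planned for.** Section 8 will explore reasons for and predictors of dropout, and will impute. That helps, but the imputation step names only caregivers of survivors, while the same section expects 40-50% mortality. Imputation is also a weaker remedy than asking.

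**Intention to treat.** A reader might see a conflict with analysis by assigned group. There is none: that principle concerns grouping regardless of adherence or crossover. The rule only reduces how many participants have T4 data.

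**Conclusion.** The point holds as a fault in the wording of the LTF rule, and the rule should be changed. Applied literally, it closes a caregiver who is unreachable around T2 or T3 at about study day 14 to 30, which is 60 to 76 days before T4 opens, and it provides no way back for T4. This rests on exactly three contacts, with the first made the day after the due day or after the window closes.

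The consequence is avoidable and possibly informative missing data in the 3-month PHQ-9, GAD-7 and PTSS. The rule is also hard to reconcile with the T4 intention in section 8, the T4-specific use of LTF, the Completed rule and the T1-linked alerts.

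It would be tempting to put a number on the T4 records lost. The documents give neither the share of caregivers who would be unreachable nor the share who would still answer at day 90, so any count would be an assumption. Differential loss by arm is likewise possible but not shown. The primary analysis of NEST at T3 is not the main concern. Whether T3 is still offered after a missed T2 is a separate inconsistency between Appendices 3 and 4.

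**What to change.** Amend the status definitions in section 5:

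1. Define non-compliance. Treat a survey that is still unanswered after three contacts and after its own window has closed as missed for that time point only.
2. Send the T4 invitation to every randomized caregiver who has not withdrawn or been withdrawn.
3. Remove the one-week re-entry limit for T4.
4. Assign final LTF status only when the T4 window closes without a response (day 90 + 28 = day 118).
5. State whether T3 is offered after a missed T2, and bring Appendix 3 (timing from T1) and Appendix 4 (T3 contingent on T2) into agreement.

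The cost is small. It needs a protocol amendment that touches the status definitions and the two appendices, and a check that the app does not suppress alerts for early non-responders. Reminders are already automated from T1, and the $15 for T4 is already in the compensation schedule. The downside is that some caregivers will receive reminders that they ignore; those who do not want them can still withdraw.

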• Aim 3: Explore family caregiver and clinician RCT experiences to characterize how these participants may have been impacted by intervention components in a variety of implementation contexts, with a goal of understanding intervention mechanisms and barriers to future implementation and dissemination. Approach and goal: Using a mixed methods approach, we will integrate findings from both qualitative analysis of semi-structured interviews via telephone with family caregivers and clinicians as well as quantitative family caregiver, patient, and care process outcomes. This will provide insight into mechanisms of action and highlight methods for future intervention optimization through enhanced personalization, replicability, and scalability—all factors that are critical to successful implementation and dissemination of the intervention.

Primary and Secondary Outcomes

All outcomes have been piloted by the Duke University study team and chosen based on the conceptual model, expert recommendations, and psychometrics (Table 1).²⁻⁴ Response burden will be minimized with short instruments and online data entry via ePRO.⁵ Pilot testing confirmed completion in 15-20 minutes and demonstrated that all outcomes were responsive at levels of clinical significance.¹ Data will be collected at pre-randomization baseline (T1 Data Collection) as well as 4 days (T2 Data Collection), 8 days (T3 Data Collection), and 3 months (T4 Data Collection) post-randomization.

Primary Outcomes

For Aim 1, usability will be assessed with the SUS ⁶ and analysis of semi-structured interview transcriptions, while acceptability will be measured with the Client Satisfaction Questionnaire (CSQ-8).⁷

For Aim 2, the primary RCT outcome will be unmet palliative care needs at T3 (8 days post-randomization) as reported by family caregivers using the Needs; Existential concerns; Symptoms; and Therapeutic interaction (NEST) scale.^{1,8,9} The NEST, which assesses palliative care needs among both critically ill older adult patients and their family caregivers (and is completed by family caregivers), is the primary trial outcome and T3 is the primary timing of its measurement.⁹ The NEST's 13 items (score range 0-130) sample each of the National Consensus Project's eight domains of palliative care quality.¹⁰ The main patient-level outcome will be the receipt of goal concordant care at T2.^{11,12}

Secondary Outcomes

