Randomization will be stratified by three variables:

Protocol Version: 5.1 Dated: 13 June 2022 Page 8 of 42

- Department location at the time of ICU admission and informed consent (i.e., Medical versus Surgical)
- Palliative Care Trigger type (i.e., Acute versus Chronic; see Appendix 2)
- Baseline NEST score (i.e., ≥25 vs. <25 but ≥10)

All family members, regardless of their randomization arm will be asked to complete a total of four surveys, as listed below (see Appendix 3 for survey timeline):

- T1: to be completed within 72 hours of informed consent; study day 1
- T2: to be completed on study day 4
- T3: to be completed on study day 8
- T4: to be completed on study day 90

Surveys are completed remotely and electronically via the web application by the enrolled family member. Reminders are automatically provided by the PCplanner platform to the family members via email and/or text alerts to complete the surveys (Appendix 4).

Patients enrolled into this study, at the consent of their legally authorized representative (LAR), will passively participate in the study. Passive participation includes allowing the study team to access and abstract relevant clinical data from the patient's EMR. The clinical data abstracted for the purposes of this research project will be housed in the secure, EDC (REDCap).

Clinicians, whether ICU attending or Palliative Care, will be asked to complete a baseline survey at the time in which informed consent is obtained. The baseline survey will collect relevant information from the clinician, such as sociodemographic and professional information, as well a contact information (e.g., email address and cell phone number). Clinicians, who are assigned to an intervention family, will receive automatic text and/or email alerts via the web application informing them of the completed survey(s), reported needs, and the need to complete a family meeting.

Aim 3

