 - Multi-system organ failure (> 3 of: lung, kidney, hematological, brain, cardiac, or liver) that has worsened over 48 hours (i.e., Sequential Organ Failure Assessment [SOFA] score increased during this time period)
- e. Severe acute stroke (e.g., acute intracranial hemorrhage, ischemic stroke, or traumatic brain injury).
- f. Acute respiratory failure, defined as any of the following:
 - i. Mechanical ventilation > 24 hours
 - ii. Any single use of O2 device, listed below, or combination of O2 devices used in 24 hours from time of ICU admission:
 - 1. Nasal cannula with O2 flow ≥ 6 liters per minute (LPM)
 - 2. Facemask oxygen (e.g., partial re-breather, non-rebreather)
 - 3. Non-invasive ventilation (BiPAP or CPAP)
 - 4. High flow nasal cannula
- g. Acute renal failure (new hemodialysis or continuous venovenous hemodiafiltration for > 1 hour)
- h. Advanced cancer (Advanced/metastatic cancer diagnosis)
- i. Shock (use of vasopressor or inotrope for > 4 hours)

Exclusion Criteria (pre-consent, patients)

- 1. Palliative care consultation performed during the hospitalization before eligibility determination.
- 2. Current admission to the ICU at the index hospital is >8 days.
- 3. Patient is imprisoned.
- 4. Patient has no known family or surrogate decision maker.
- 5. Death is expected to occur within 24 hours.

Exclusion Criteria (post-consent, patients)

1. Patient dies before T1 completion.

Family members

Inclusion Criteria (pre-consent, family member)

- 1. Family member is > 18 years of age.
- 2. Self-described as the individual (related or unrelated) who provides the most support and with whom the patient has a significant relationship (per definition of 'family' described in the Society of Critical Care Medicine 2016 Guidelines for Family-Centered Care in the Neonatal, Pediatric, and Adult ICU).

Protocol Version: 5.1 Dated: 13 June 2022 Page **10** of **42**

Exclusion Criteria (pre-consent, family member)

- 1. Lack of English fluency such that the potential participant and/or study team is not confident that they could complete study tasks (app viewing, surveys).
- 2. Family member is imprisoned.
- 3. Family member is unable to complete study surveys for any reason.

Exclusion Criteria (post-consent, family member)

1. Low need burden (NEST score < 10) at the completion of survey 1 (T1).

Clinicians

Inclusion Criteria (ICU Physicians)

- 1. ≥18 years of age.

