- Randomized: defined as any family member who's loved one has the statuses of RELEASED, APPROVED, and CONSENTED, the family member completes T1 survey, and continues to meet all eligibility criteria. Family members who reach this status will be required to interact with the app three additional times (i.e., completion of T2, T3, and T4). Additionally, if the family is randomized to Arm 1, they will be required to participate in at least one family meeting conducted by the ICU attending. Patients and family members who are assigned this status must be maintained on the enrollment log.
 - Responder: defined as any family member who is randomized to the intervention arm and upon completing survey 2 (T2) received a NEST score of <25 and their survey 2 (T2) score is less than their survey 1 (T1) score. Individuals who are assigned this study status will not receive a Palliative Care consult by the Palliative Care clinician. Only the ICU attending will be able to view the survey results.

 - Non-responder: defined as any family member who is randomized to the intervention arm and upon completing survey 2 (T2) received a NEST score of >25 or their survey 2 (T2) score is greater than their survey 1 (T1) score. Individuals who are assigned this study status are to receive a Palliative Care consult by the Palliative Care clinician. The family member's survey results will be viewed by both the ICU attending and the Palliative Care clinician.
- Screen Failed: defined as any family member who was consented to the study, completes survey 1 (T1), but DOES NOT receive a NEST score of ≥ 10 on completion of survey 1 (T1). Patients and their family members who are assigned this status must be maintained on the enrollment log.
- Withdraw by PI or Self: defined as any family member who voluntarily consents to participate in the study, but is then withdrawn from the study. The PI may withdraw a participate at any time without their consent if the PI deems it is in their best interest to no longer participate OR the individual demonstrates lack of compliance with study protocol and study procedures. Family members who reach this status have no additional follow-ups or study requirements; no further clinical data will be abstracted from the patient's EMR. Patients and family members who are assigned this status must be maintained on the enrollment log.
- Lost to Follow-Up (LTF): defined as any family member who voluntarily consents to participate

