We will test the primary study hypothesis that the NEST score is lower (i.e., fewer unmet needs) for intervention family caregivers compared to usual care at T3 (~1-week post-randomization). All participants will be analyzed as part of the group they were assigned, regardless of adherence or crossover status (i.e., intention to treat). We will use a general linear model to estimate mean NEST changes and corresponding confidence intervals over time using SAS PROC MIXED (SAS Institute, Cary NC). Different correlation structures will be examined (e.g., unstructured, autoregressive) and model fit indices will be used to guide the choice of the final model's structure.

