Analyses similar to those conducted for the NEST (primary outcome analyses) above will be performed for the secondary family caregiver hypotheses involving PHQ-9, GAD-7, and PTSS scores at T3 and T4. While family caregivers will be interviewed at T4 regardless of patient survival, patient death could complicate the analyses in two key ways: (1) Presence of missing data due to family loss to follow up (i.e., non-random missing data) and (2) differences in family caregiver distress by patient survival status (i.e., heterogeneous effect). 35 To address the impact of patient death on outcomes, after first exploring reasons for and predictors of dropout, we will conduct a 2-step supplemental analysis. In Step 1, missing T4 data due to loss to follow up among family caregivers of survivors will be multiply imputed via SAS PROC MI. In Step 2, we will account for T4 outcomes that are missing due to death via composite endpoint and principal stratification methods to estimate the causal effects of the intervention in the presence of these unidentified outcomes and complicated missing data patterns. 36,37 For the key patient outcome, receipt of goal concordant care, we will use logistic regression models adjusting for the stratification variables, to examine if rates at T3 differ by treatment group. The key healthcare systems outcome, post-randomization hospital length of stay (LOS), provides a unique challenge due to the high expected mortality rate (40-50%). In addition to descriptive analyses, steps to examine treatment group LOS differences will include: (1) a proportional hazards model with death treated as a censoring event; (2) a chi-square test of mortality rate differences; and (3) a Brunner-Manzel rank test for the composite death-LOS outcome. This last step implements a recently developed methodology of a composite outcome that incorporates a numerical value for death (i.e., coded as the worst possible outcome or the longest possible stay) in the observed LOS distribution. 38,39

Aim 3

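### The primary NEST model states no baseline or stratification adjustment. Against an unadjusted change analysis, stating it would add about 1 to 7 points of power at 8.80 if the T1 SD is 0.8 to 1.0 of the T3 SD.

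*Combined protocol and SAP*

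**What the plan says.** Section 8 (Aim 2) of the combined protocol and SAP puts the primary hypothesis at T3. It then gives the model in one sentence: "We will use a general linear model to estimate mean NEST changes and corresponding confidence intervals over time using SAS PROC MIXED". The only further model choice it describes is the correlation structure, to be picked by fit.

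Other parts of the document bear on this:

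- **Randomization (section 3, Aim 2).** "Randomization will be stratified by three variables": department, trigger type and "Baseline NEST score (i.e., ≥25 vs. <25 but ≥10").
- **Availability of T1 NEST (section 5, definition of Randomized).** A caregiver is randomized only when "the family member completes T1 survey, and continues to meet all eligibility criteria". Every randomized caregiver therefore has a T1 NEST score.
- **Exclusion (section 4, post-consent, family member).** "Low need burden (NEST score < 10) at the completion of survey 1 (T1"). This truncates the T1 distribution from below.
- **Goal-concordant care (section 8, Aim 2).** "we will use logistic regression models adjusting for the stratification variables, to examine if rates at T3 differ by treatment group". This is the only analysis for which adjustment is stated.
- **PHQ-9, GAD-7 and PTSS (section 8, Aim 2).** "Analyses similar to those conducted for the NEST (primary outcome analyses) above will be performed for the secondary family caregiver hypotheses". Appendix 5 shows all three measured at T1.
- **Sample Size and Power (section 8).** 65 per arm, SD 21.1 and correlation 0.64 give 80% power for a NEST difference of 8.80, from a mixed-model difference-in-slopes calculation. For PHQ-9, SD 5.3 and correlation 0.6 give 2.33.

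**The concern.** On the plain reading, T1 NEST enters the primary analysis only by being subtracted. Subtraction gives baseline a coefficient of exactly 1. Least squares would give it the correlation times the ratio of the T3 SD to the T1 SD, which is 0.64 when the SDs are equal. The gap between these coefficients is lost precision.

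There is a second effect. Because randomization is stratified by baseline NEST, the arms are partly balanced on a variable related to the change score. An analysis that ignores this reports a standard error larger than the true one, so its intervals are somewhat too wide and its test somewhat conservative.

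Neither effect causes bias, and neither undermines the planned 80% power. What is at stake is a gain that needs no extra participants or data, together with a primary test fixed before the outcomes are seen. The same wording carries over to the three distress scales.

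**Working it through.** **Inputs.** From Sample Size and Power: 65 per arm, SD 21.1 (taken as the T3 SD; its time point is not stated), correlation rho = 0.64, 5% type I error (taken as two-sided, which reproduces the plan's figure), 80% power. Write k for T1 SD / T3 SD. The documents do not give k, and the NEST <10 exclusion may put it below 1.

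**Formulas.**
- Change-score variance = SD² × (1 + k² − 2·rho·k)
- Baseline-adjusted variance = SD² × (1 − rho²)
- SE = sqrt(variance × 2/65); detectable difference = 2.8016 × SE

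**Reproducing the plan.** With k = 1, the change SD is 21.1 × sqrt(0.72) = 17.90, the SE is 3.141 and the detectable difference is 8.80. For PHQ-9 the change SD is 5.3 × sqrt(0.8) = 4.74, the SE is 0.832 and the detectable difference is 2.33. Both match the plan.

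Adjusted, the NEST SD is 21.1 × sqrt(0.5904) = 16.21, the SE is 2.844 and the detectable difference is 7.97. For PHQ-9 the adjusted SE is 0.744 and the detectable difference is 2.08. Neither matches, so the sizing is that of an unadjusted change contrast.

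**The difference-in-slopes option.** With visits at days 0, 4 and 8, arm-specific intercepts and equal SDs, the generalized least squares slope times 8 puts weights −1, 0, +1 on T1, T2, T3 under compound symmetry or AR(1). That is T3 minus T1. If T1 is placed on study day 1, the detectable difference becomes 8.77 or 8.73.

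**Nominal power at 8.80.** Adjusted power is 87.2% in every row.

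| k | Change SE | Change power | Gain (points) | Variance ratio, adjusted/change |
|---|---|---|---|---|
| 1.0 | 3.141 | 80.0% | 7.2 | 0.82 |
| 0.9 | 3.002 | 83.4% | 3.7 | 0.90 |
| 0.8 | 2.905 | 85.8% | 1.4 | 0.96 |
| 0.64 | 2.844 | 87.2% | 0 | 1.00 |

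At k = 1 the nominal 95% half-width falls from 6.16 to 5.57, and 54 per arm would give 80% power.

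**Allowing for stratified randomization.** The nominal variance ratio overstates the benefit, because stratification already captures part of it. A simulation used 130 participants and 10,000 trials per setting, and assumed:
- permuted blocks of 4 within the eight strata;
- department and trigger type split 50/50 and unrelated to outcome;
- T1 = 10 plus a gamma variable, with T1 mean 30, 35 or 40;
- complete data.

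The adjusted model was T3 on arm, T1, department and trigger type.

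| k | Unadjusted power | Adjusted power | Gain (points) | True variance ratio |
|---|---|---|---|---|
| 1.0 | 79.6-80.5% | 86.3-86.9% | 6-7 | 0.87-0.90 |
| 0.9 | 82.8-83.7% | 85.9-86.8% | about 3 | 0.94-0.95 |
| 0.8 | 85.2-85.4% | 86.1-86.8% | about 1 | about 0.98 |

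At k = 1 the unadjusted analysis reports an SE of about 3.14 against a true 3.01-3.03, with type I error of 4.0-4.3%. Adjusted type I error is 4.8-5.4%. Monte Carlo error is about 0.4 points for power and 0.2 for type I error.

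**PHQ-9 (nominal, not simulated).** Adjusted power at 2.33 is 88.0%, against 80.0%, 83.5% and 86.0% for the change score at k = 1, 0.9 and 0.8.

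**The case against.** The plan is silent rather than wrong. A PROC MIXED analysis of NEST over time is compatible with an equal-baseline model. If that is what the analyst runs, there is nothing to gain, and sizing on a change score does not bind the analysis to one. This stands: the gain is measured against an unadjusted T3−T1 contrast, which is inferred from the reference to changes and from the sizing. Silence has its own cost, though. An unadjusted comparison of T3 scores alone is also compatible with the stated hypothesis, and its power at 8.80 is only 66.2% (SE 3.701).

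The slope equivalence is limited. The plan lists an unstructured correlation first. With assumed T1-T2/T2-T3 correlations of 0.75/0.6 or 0.7/0.85, a linear slope has detectable differences of 8.50 or 8.27, so part of the loss disappears. This also stands.

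The ratio k is unknown. The nominal gain is 0.2 points at k = 0.7 and 11.5 at k = 1.1. If 21.1 is the T1 SD instead, the gain is 4.4 points at k = 0.9 and 1.8 at k = 0.8, though power before and after is then lower. The block size, the T1 distribution and complete follow-up are assumptions too.

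Finally, the plan meets its own power target without any change. That makes this a recommended improvement, not a defect that threatens the trial. None of these points is a reason to leave the model unspecified.

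**Conclusion.** The concern holds. The primary model is stated without baseline or stratification adjustment, and the plan's own detectable differences are those of an unadjusted change contrast. Against that contrast, adjustment adds about 6 to 7 points of power at 8.80 if the T1 and T3 SDs are equal, about 3 points at a ratio of 0.9, about 1 point at 0.8, and nothing at 0.64. These figures rest on 21.1 being the T3 SD, a correlation of 0.64, complete data on 65 per arm and the simulation settings above. Any gain from department and trigger type cannot be computed from the documents and is not counted. There is no bias, and the 80% power at 8.80 stands for the change contrast. The plan should make this change, but the trial's validity does not depend on it.

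**What to change.** In section 8 (Aim 2), name the primary test as the treatment difference at T3 and commit to one of these repeated-measures models:

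- **(a)** T2 and T3 NEST as responses, with categorical visit, treatment-by-visit, continuous T1 NEST and T1 NEST-by-visit; or
- **(b)** T1, T2 and T3 NEST as responses, with arm means constrained equal at T1 and T1 not also entered as a covariate.

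In complete-data simulations the two gave the same T3 estimate as regressing T3 on arm and T1. They treat missing follow-up differently: (a) drops a caregiver with neither T2 nor T3, while (b) keeps that caregiver's T1. The choice should therefore be written down in advance. In (a), keep the T1-by-visit term; leaving it out raised the SD of the estimate from 2.843 to 2.886 in one of three assumed correlation settings and by 0.002 in the others.

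Include department and trigger type as covariates because they are randomization strata. Use the same form for PHQ-9, GAD-7 and PTSS, with T3 and T4 as follow-up responses and each scale's own T1 score. Keep 8.80 as a conservative detectable difference.

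The cost is analysis wording only. T1 scores, department and trigger type are recorded before randomization, and the sample size does not change.
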